## PROTOCOL SYNOPSIS

### PROTOCOL NO.: SIGA-246-024

**TITLE:** A Double-Blind, Randomized, Placebo-Controlled, Multicenter Study to Assess the Safety, Tolerability, and Pharmacokinetics of TPOXX® When Administered Orally for 28 Days in Adult Subjects

**STUDY PHASE:** 3

**STUDY SITES:** [REDACTED]

### OBJECTIVES:

#### Primary:

The primary objective of this study is to determine the safety and tolerability of TPOXX when administered orally for 28 days in adult subjects.

#### Secondary:

The secondary objective of this study is to describe the pharmacokinetic (PK) profile of TPOXX when administered orally for 28 days in adult subjects.

### STUDY DESIGN AND METHODOLOGY:

This is a Phase 3, multicenter, double-blind, randomized, placebo-controlled study to assess the safety, tolerability, and PK of oral TPOXX 600 mg when administered orally for 28 days in adult subjects.

A total of at least 445 subjects (includes a PK subset of 40 subjects), ages 18 to 80, inclusive, will be enrolled and randomly assigned within stratified age groups (18 to 30 years, 31 to 45 years, 46 to 64 years, and 65 to 80 years) to 1 of 2 treatment groups in an overall randomization of 4:1 (approximately 356 subjects will receive TPOXX and 89 subjects will receive TPOXX matching placebo). There will be 2 dosing regimens based on the subject's body weight: subjects with a body weight of 120 kg or less will be administered either TPOXX 600 mg or placebo two times a day (BID), 12 hours apart ( $\pm$ 30 minutes); and subjects with a body weight more than 120 kg will be administered either TPOXX 600 mg or placebo three times a day (TID), 8 hours apart ( $\pm$ 30 minutes). The enrollment goal for the study is to randomly assign a sufficient number of subjects to ensure that at least 300 subjects receive at least 92% of the oral TPOXX 600 mg BID or TID dosing regimen over the 28-day treatment period. Overall, across all clinical investigative sites, a goal of approximately 20% of subjects (i.e., 89 subjects) or more will be enrolled and randomly assigned in each age group to ensure a respective investigation of TPOXX safety and PK across age groups. The treatment groups will be as follows:

- Treatment Group 1: An oral dose of 600 mg ( $3 \times$  200-mg capsules) TPOXX BID (every 12 hours [ $\pm$ 30 minutes]) for subjects with a body weight of 120 kg or less or TID (every 8 hours [ $\pm$ 30 minutes]) for subjects with a body weight more than 120 kg for 28 days (Day 1 to Day 28).

- Treatment Group 2: An oral dose of placebo (3 capsules identical to TPOXX) BID (every 12 hours [ $\pm$ 30 minutes]) for subjects with a body weight of 120 kg or less or TID (every 8 hours [ $\pm$ 30 minutes]) for subjects with a body weight more than 120 kg for 28 days (Day 1 to Day 28).

When study drug is administered at the clinical investigative site, all subjects will be provided a meal (consisting of approximately 600 calories and 25 g of fat). The meal should be consumed within 30 minutes and prior to the administration of study drug (TPOXX or matching placebo). Subjects should be administered study drug as soon as possible following completion of the meal but no more than 30 minutes should elapse between meal completion and administration of study drug. Subjects should take study drug with 8 oz. (240 mL) of water. Subjects will be instructed at the screening visit and prior to check-in to the clinical investigative site on either Day –1 or Day 1 that other than water, no beverages may be ingested within 3 hours before or 3 hours after study drug administration.

When study drug (TPOXX or matching placebo) is administered at home, subjects will be instructed to take it within 30 minutes after the completion of a meal consisting of approximately 600 calories and 25 g of fat and with 8 oz. (240 mL) of water. Other than water, no beverages may be ingested within 3 hours before or 3 hours after taking study drug, excluding a beverage that is being consumed as a part of the required meal.

Clinical investigative sites will provide subjects with instructions and dietary information in order to help them meet the study requirement for eating meals with an appropriate caloric and fat content before study drug dosing.

Clinical investigative sites will provide subjects with a subject diary and instructions to record the time that they completed their last meal before taking study drug in the subject diary. Subjects will be instructed to record that they have met the required caloric and fat intake of eating a meal containing approximately 600 calories and 25 g of fat before each dose of study drug.

Clinical investigative sites will instruct subjects to record the time that they take study drug in their subject diary. Subjects will follow a dosing regimen of study drug appropriate for their weight for 28 days and will be instructed to take their study drug at the same time of the day each day.

Safety assessments will include clinical laboratory test results (hematology, serum chemistry, and urinalysis), monitoring of adverse events (AEs) including serious AEs (SAEs), vital sign measurements (systolic and diastolic blood pressures, heart rate, respiratory rate, and body temperature), electrocardiogram (ECG) results, and physical examination findings.

All subjects will have a follow-up telephone call 14 and 30 days after the last dose of study drug (Day 42 [+2 days] and Day 58 [+2 days], respectively) to report any AEs and SAEs. All AEs, SAEs, and clinically significant laboratory abnormalities will be followed until resolution or until stability of the abnormality has been demonstrated as determined by the investigator and/or medical monitor.

The study will consist of a screening period (Day -28 to Day -2), 1 check-in, on-site visits (Day 7, Day 14, and Day 21), a dosing complete/early termination (ET) visit (Day 29), and 2 follow-up telephone calls (Day 42 [+2 days] and Day 58 [+2 days]).

The total duration of the study for each subject, including screening, treatment, and follow-up telephone calls, will be approximately 86 days.

**Non-PK Study Subjects:**

Those subjects not participating in the PK subset will check into the clinical investigative site in the morning of Day 1 and will remain at the clinical investigative site until after the first dose on Day 1 and all safety assessments have been completed.

With the exception of the first dose of study drug administered at the clinical investigative site on Day 1, subjects will administer study drug at home for all remaining doses through Day 28.

**PK Subset Study Subjects:**

Those subjects participating in the PK subset will follow the same general schedule with the addition of several overnight stays. Specifically, the PK subset will consist of a screening period (Day -28 to Day -2), 3 check-in and in-house periods (Day -1 to Day 2; Day 13 to Day 14; and Day 27 to Day 31), a dosing complete/ET visit (Day 29), and 2 follow-up telephone calls (Day 42 [+2 days] and Day 58 [+2 days]).

Subjects in the PK subset will check into the clinical investigative site on Day -1, Day 13, and Day 27 and be discharged from the clinical investigative site on Day 2, Day 14, and Day 31. Subjects will check into the clinical investigative site early enough to eat the required meal and then be administered the final dose for that day on Day 13 and Day 27.

When the study drug is not administered at the clinical investigative site, subjects will administer study drug at home.

Serial blood samples for PK analysis of TPOXX will be collected before the first dose of study drug (0 hour) on Days 1, 14, and 28 and up to 24 hours after study drug administration on Day 1 and up to 72 hours after the first dose of study drug on Day 28.

**STUDY POPULATION:**

**Inclusion Criteria:**

Each subject must meet all of the following criteria to be enrolled in this study:

1. Subject is male or female between 18 and 80 years of age, inclusive.
2. Subject is available for clinical follow-up for the duration of the study.
3. Women of childbearing potential have a negative  $\beta$ -human chorionic gonadotropin pregnancy test (serum) at the screening visit and a negative urine pregnancy test on Day 1 or Day -1 (PK subset) before receipt of study drug, and meet one of the following criteria:

- a. Subject or their partner has undergone surgical sterilization.
- b. Male sexual partner who has undergone a vasectomy at least 3 months before screening.
- c. Subject is postmenopausal, defined as 12 consecutive months with no menses without an alternative medical cause and has a documented plasma follicle-stimulating hormone level >40 IU/mL.
- d. Subject agrees to be abstinent (i.e., heterosexually inactive) for the duration of the study.
- e. Subject agrees to consistently use 1 of the following methods of contraception from the beginning of screening (which they had been consistently using for at least 30 days before the first dose of study drug) through 30 days after the last dose of study drug:
  - i. Condoms, male or female, with a spermicide

**NOTE:** For male subjects, condoms must be used for 90 days after the last dose of study drug. Male and female condoms should not be used together, as this can reduce their effectiveness.

- ii. Diaphragm or cervical cap with spermicide
- iii. Intrauterine device with spermicide
- iv. Oral contraceptives or other hormonal methods

**NOTE:** Another nonhormonal method of contraception must be used in conjunction with oral contraceptives.

4. Male subjects must agree to not donate sperm from the first dose of study drug through 90 days after the last dose of study drug.
5. Subject is considered by the investigator to be in good general health as determined by medical history (no hospitalizations for chronic medical conditions in the previous 2 years), clinical laboratory test results, vital sign measurements, 12-lead ECG results, and physical examination findings at screening.
6. Subject agrees not to use nicotine products, including electronic vapor cigarettes, nicotine patches, or nicotine gum, for at least 30 days before the Day 1 randomization visit through completion of the Day 29 dosing complete/ET visit.
7. Subject agrees to comply with the study dietary requirements throughout the study drug dosing period.
8. Subject agrees not to consume caffeine- or xanthine-containing products during all study visits, including overnight stays (PK subset); sodas, coffee, and tea designated as caffeine-free or noncaffeinated may be consumed on study days; caffeine may be consumed while at home and between study visits.
9. Subject agrees to comply with all protocol requirements.
10. Subject has adequate venous access if participating in the PK subset.
11. Subject is able and willing to provide written informed consent.

**Exclusion Criteria:**

Subjects meeting any of the following criteria will be excluded from the study:

1. Subject is a female who is pregnant or breastfeeding or planning to become pregnant within 3 months after the last dose of study drug.
2. Subject has a history of any clinically significant conditions including:
  - Asthma treated with oral systemic steroids within the past 6 months
  - Diabetes mellitus (type 1 or 2), with the exception of gestational diabetes
  - Thyroidectomy or thyroid disease that required medication within the past 12 months
  - Serious angioedema episodes within the previous 3 years or requiring medication in the previous 2 years
  - History of head trauma resulting in a diagnosis of traumatic brain injury other than concussion
  - Frequent episodes of headache
3. Subject has received any vaccination within 28 days prior to Day 1 or plans to receive a vaccination at any time during the treatment period or within 28 days after study Day 28.
4. Subject has received treatment in another clinical study of an investigational drug (or medical device) or investigational vaccine within 30 days or 5 half-lives (whichever is longer) before the first dose of study drug.
5. Subject has a history of relevant drug and/or food allergies (i.e., allergy to TPOXX or excipients, or any significant food allergy that could preclude a standard diet in the clinical investigative site).
6. Subject has any condition possibly affecting drug absorption (e.g., previous surgery on the gastrointestinal tract, including removal of parts of the stomach, bowel, liver, gallbladder, or pancreas, with the exception of appendectomy).
7. Subject has evidence or history of clinically significant allergic reaction (excluding seasonal allergies); or has evidence or history of clinically significant disease, including hematological, endocrine, pulmonary, gastrointestinal, cardiovascular, hepatic, psychiatric, or neurological disease. Exceptions to these disease criteria (e.g., stable, mild joint disease unassociated with collagen vascular disease) may be made following discussions with the medical monitor.
8. Subject has a history of cardiac disease, symptomatic or asymptomatic arrhythmias, syncopal episodes, chest pain (that is diagnosed as cardiac related) or trouble breathing on exertion, or risk factors for torsades de pointes (e.g., heart failure, hypokalemia).
9. Subject has a family history of an immediate family member (father, mother, brother, or sister) who has had an onset of ischemic heart disease before the age of 50 years.
10. Subject is 20 years of age or older and has a  $\geq 30\%$  risk of developing a myocardial infarction or coronary death within the next 10 years using the National Cholesterol Education Program's Risk Assessment Tool: <https://www.mcw.edu/calculators/ldl-cholesterol-goal-level>.

11. Subject has a seizure disorder or history of seizures (does not include childhood febrile seizures) or a past history that increases seizure risks such as significant head injury that caused loss of consciousness or other changes in the subject's daily function, concussion, stroke, central nervous system infection or disease, or alcohol or drug abuse or family history of idiopathic seizures.
12. Subject has a history of a peptic ulcer or significant gastrointestinal bleeding.
13. Subject has a bleeding disorder diagnosed by a doctor (e.g., factor deficiency, coagulopathy, or platelet disorder requiring special precautions) or significant bruising or bleeding difficulties with blood draws.
14. Subject has a malignancy that is active or treated malignancy for which there is not reasonable assurance of sustained cure, or malignancy that is likely to recur during the period of the study (subject should be in complete remission for at least 5 years).
15. Subject has neutropenia or other blood dyscrasia determined to be clinically significant by the investigator.
16. Subject has used any of the following prohibited medications from within 7 days (or 5 half-lives, whichever is longer) before the first dose of study drug: antidiabetic medication; anticoagulants; anticonvulsants; substrates of the breast cancer resistance protein transporter including methotrexate, mitoxantrone, imatinib, irinotecan, lapatinib, rosuvastatin, sulfasalazine, and topotecan; substrates of cytochromes (CYP)2C8 including repaglinide, paclitaxel, montelukast, pioglitazone, rosiglitazone; and substrates of CYP2C19 including S-mephénytoin, clobazam, diazepam, rabeprazole, voriconazole, lansoprazole, and omeprazole. Medications not listed here that are known (or thought) to be CYP3A4 substrates may be allowed at the investigator's discretion, after consultation with the medical monitor, if administration poses little to no risk to the subject.
17. Subject has a history of drug or alcohol abuse or dependency within the last year before screening.
18. Subject has a current or recent (<30 days before screening) history of clinically significant bacterial, fungal, or mycobacterial infection.
19. Subject has a current clinically significant viral infection.
20. Subject has a known clinically significant chronic viral infection (e.g., human T cell lymphotropic virus I or II).
21. Subject demonstrates long-term use ( $\geq 14$  consecutive days) of glucocorticoids, including oral or parenteral prednisone or equivalent ( $>20$  mg total dose per day), or high-dose inhaled steroids ( $>800$  mcg/day of beclomethasone dipropionate or equivalent) within the preceding 1 month (low-dose [ $\leq 800$  mcg/day of beclomethasone dipropionate or equivalent] inhaled and topical steroids are allowed).
22. Subject has donated  $>450$  mL blood or blood components within 30 days before the first dose of study drug. The investigator should instruct subjects who participate in this study to not donate blood or blood components for 4 weeks after the completion of the study.
23. Subject reports participation in strenuous activity or contact sports within 24 hours before the first dose of study drug.

24. Subject has known hepatitis B or C infection or positive test for hepatitis B surface antigen, hepatitis C virus antibody, or human immunodeficiency virus type 1 or 2 antibodies at screening.
25. Subject has a positive test result for amphetamines (including methamphetamines and ecstasy/methylenedioxymethamphetamine), barbiturates, benzodiazepines, cannabinoids (including tetrahydrocannabinol), cocaine metabolites, opiates (including heroin, codeine, and oxycodone), cotinine, or alcohol at screening or check-in.
26. Subject has any of the following laboratory test results within 28 days before the first dose of study drug:
  - Estimated serum creatinine clearance (Cockcroft-Gault) <70 mL/min
  - Creatinine in males >1.7 mg/dL and in females >1.4 mg/dL (1.3 times the upper laboratory reference range)
  - Hemoglobin ≤10% of the lower laboratory reference range
  - White blood cell counts considered to be clinically significant by the investigator
  - Absolute neutrophil count <1000 cells/mm^3
  - Platelets not within ±10% of laboratory reference range
  - Alanine aminotransferase >2 times above the upper laboratory reference range
  - Aspartate aminotransferase >2 times above the upper laboratory reference range
  - Alkaline phosphatase >20% above the upper laboratory reference range
  - Hemoglobin A1c ≥7.0%
  - Cholesterol ≥300 mg/dL and low-density lipoprotein ≥190 mg/dL
27. Subject has hypertension that is poorly controlled (repeat reading >140 mm Hg systolic and/or >90 mm Hg diastolic) or blood pressure considered to be clinically significant by the investigator. Blood pressure may be retested twice in the sitting position at 5-minute intervals.
28. Subject has a resting heart rate of <40 beats per minute or >110 beats per minute at screening.
29. Subject has an abnormal ECG at screening that is determined by the investigator to be clinically significant.
30. Male subject has a QT interval corrected using Fridericia's formula (QTcF) >450 ms or female subject has a QTcF >470 ms at screening or Day 1 or Day -1 (PK subset).
31. Subject has used any prescription antiviral drugs with the intention of coronavirus disease (COVID-19) treatment or prophylaxis, including those that are thought to be effective for prevention of COVID-19 but have or have not been licensed for this indication, within 1 month prior to study entry or during the study.
32. In the opinion of the investigator, the subject is not suitable for entry into the study.
33. Subject is a member or family member of the investigator or study site personnel.
34. Subject has previously participated in this clinical trial.

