17. Subject has a history of drug or alcohol abuse or dependency within the last year before screening.
18. Subject has a current or recent (<30 days before screening) history of clinically significant bacterial, fungal, or mycobacterial infection.
19. Subject has a current clinically significant viral infection.
20. Subject has a known clinically significant chronic viral infection (e.g., human T cell lymphotropic virus I or II).
21. Subject demonstrates long-term use ( $\geq 14$  consecutive days) of glucocorticoids, including oral or parenteral prednisone or equivalent ( $>20$  mg total dose per day), or high-dose inhaled steroids ( $>800$  mcg/day of beclomethasone dipropionate or equivalent) within the preceding 1 month (low-dose [ $\leq 800$  mcg/day of beclomethasone dipropionate or equivalent] inhaled and topical steroids are allowed).

22. Subject has donated >450 mL blood or blood components within 30 days before the first dose of study drug. The investigator should instruct subjects who participate in this study to not donate blood or blood components for 4 weeks after the completion of the study.
23. Subject reports participation in strenuous activity or contact sports within 24 hours before the first dose of study drug.
24. Subject has known hepatitis B or C infection or positive test for hepatitis B surface antigen, hepatitis C virus antibody, or human immunodeficiency virus type 1 or 2 antibodies at screening.
25. Subject has a positive test result for amphetamines (including methamphetamines and ecstasy/methylenedioxymethamphetamine), barbiturates, benzodiazepines, cannabinoids (including tetrahydrocannabinol), cocaine metabolites, opiates (including heroin, codeine, and oxycodone), cotinine, or alcohol at screening or check-in.
26. Subject has any of the following laboratory test results within 28 days before the first dose of study drug:
  - Estimated serum creatinine clearance (Cockcroft-Gault) <70 mL/min
  - Creatinine in males >1.7 mg/dL and in females >1.4 mg/dL (1.3 times the upper laboratory reference range)
  - Hemoglobin  $\leq$ 10% of the lower laboratory reference range
  - White blood cell counts considered to be clinically significant by the investigator
  - Absolute neutrophil count <1000 cells/mm^3
  - Platelets not within  $\pm$ 10% of laboratory reference range
  - Alanine aminotransferase >2 times above the upper laboratory reference range

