## 6.2.2 Clinical Laboratory Testing

Blood and urine samples will be collected at the time points indicated in the schedules of events (Table 9-1 and Table 9-2) and will be prepared using standard procedures. Samples for safety testing will be shipped via courier to PPD Central Lab where they will be analyzed. The central laboratory for the study will receive, test, and store laboratory safety samples at the following location:

Repeat clinical laboratory tests may be performed at the discretion of the investigator, if necessary, to evaluate inclusion and exclusion criteria or clinical laboratory abnormalities. PPD Central Lab will provide the reference ranges for all clinical laboratory safety parameters.

The following clinical laboratory assessments will be performed by the PPD Central Lab:

Hematology	Hematocrit, hemoglobin, mean corpuscular hemoglobin, mean corpuscular hemoglobin concentration, total and differential leukocyte count (basophils, eosinophils, lymphocytes, monocytes, neutrophils), mean corpuscular volume, platelet count, red blood cell count, and red cell distribution width
Serum Chemistry	Alanine aminotransferase, albumin, alkaline phosphatase, anion gap, aspartate aminotransferase, bilirubin (total), blood urea nitrogen, calcium, carbon dioxide, chloride, creatinine, creatinine clearance (calculated (a) ), gamma-glutamyltransferase, globulin, glucose, lactate dehydrogenase, phosphorus, potassium, sodium, total protein, and uric acid
Urinalysis	Appearance, bilirubin, blood, color, glucose, ketones, leukocyte esterase, microscopy (performed if dipstick is $\geq 1+$ ; includes bacteria, casts, crystals, epithelial cells, red blood cells, and white blood cells), nitrites, pH, protein, specific gravity, and urobilinogen

(a) Creatinine clearance will be calculated using the Cockcroft-Gault formula:

$$\text{Creatinine clearance (mL/min)} = \frac{[140 - \text{age (years)}] \times \text{weight (kg)}}{72 \times \text{serum creatinine (mg/dL)}} \{ \times 0.85 \text{ if female} \}$$

Glycosylated hemoglobin and a fasting lipid panel including cholesterol (total, high-density lipoprotein, calculated low-density lipoprotein, and triglycerides) will be performed at

screening. Subjects will fast for 8 hours prior to specimen collection of the fasting lipid panel.

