- (h) Includes alcohol, cotinine, amphetamines (including methamphetamines and ecstasy/methylenedioxymethamphetamine), barbiturates, benzodiazepines, cannabinoids (including tetrahydrocannabinol), cocaine metabolites, and opiates (including heroin, codeine, and oxycodone). A urine drug screen including alcohol and cotinine will be collected and sent to the central laboratory at the screening visit. A urine drug screen and alcohol breath test using a breathalyzer will be performed and read locally on Day -1.
- (i) Fasting lipid panel will include cholesterol (total, high-density lipoprotein, calculated low-density lipoprotein, and triglycerides). Fasting shall occur for 8 hours prior specimen collection.
- (j) Clinical laboratory testing will include hematology, serum chemistry, and urinalysis. Clinical laboratory testing from screening will be used to determine eligibility.
- (k) Women of childbearing potential only. A urine pregnancy test will be performed and read locally on Day -1. All other pregnancy tests, including screening, are by serum and read by the Central Lab.
- (l) For postmenopausal women.
- (m) A single 12-lead ECG will be obtained after the subject has been in the supine position for at least 10 minutes. On Day 1 and Day 14, an ECG will be recorded within 60 minutes prior to the first dose of the day and 4 hours after the first dose of the day. The acceptable window for collection from the scheduled collection time point is  $\pm 15$  minutes.
- (n) When study drug is administered at the clinical investigative site, all subjects will be provided a meal (consisting of approximately 600 calories and 25 g of fat). The meal should be consumed within 30 minutes and prior to the administration of study drug (TPOXX or matching placebo). Subjects should be administered study drug as soon as possible following completion of the meal but no more than 30 minutes should elapse between meal completion and administration of study drug. Subjects should take study drug with 8 oz. (240 mL) of water.
- (o) The time of study drug dosing will be called "0" hour. Study drug will be administered to subjects by study site personnel when subjects are in house and subjects will self-administer study drug when at home.

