## **9.3 APPENDIX 3: STUDY GOVERNANCE**

### **9.3.1 Data Quality Assurance**

This study will be conducted using the quality processes described in applicable procedural documents. The quality management approach to be implemented will be documented and will comply with current ICH guidance on quality and risk management. All aspects of the study will be monitored for compliance with applicable government regulatory requirements, current Good Clinical Practice (GCP), the protocol, and SOPs. The monitor will maintain current personal knowledge of the study through observation, review of study records and source documentation, and discussion of the conduct of the study with the investigator and staff. Electronic case report forms (eCRFs) and electronic data capture will be utilized. The electronic data capture system is validated and compliant with US Title 21 CFR Part 11. Each person involved with the study will have an individual identification code and password that allows for record traceability. There may be an internal quality review audit of the data and additional reviews by the clinical monitor.

Steps to be taken to ensure the accuracy and reliability of data include, but are not limited to: selection of qualified investigators and appropriate clinical investigative sites, protocol training and review of protocol procedures with the investigators and study site personnel before the start of the study, site initiation and periodic interim monitoring visits by PPD, and direct transmission of safety laboratory data into the PPD study database for all clinical safety laboratory tests performed. The eCRF will be reviewed for accuracy and completeness by a PPD clinical research associate (CRA) during on-site monitoring visits. Discrepancies will be resolved with the investigators or designees, as appropriate. The data will be entered into the clinical study database and validated for accuracy. During on-site monitoring visits, 100% source documentation verification will be performed. SIGA or the Joint Program Executive Office for Chemical, Biological, Radiological and Nuclear Defense representatives may accompany the PPD CRA on any scheduled site visit. Investigators will be informed in advance of any visitors to the clinical investigative site in addition to the PPD CRA.

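### Exclusion 26 sets the haemoglobin limit at one tenth of the lower reference limit, so the only numeric haemoglobin entry rule excludes nobody; about 0.90 x the limit is the probable intent

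*Combined protocol and SAP*

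**What the plan says.** Criterion 26 lists laboratory results that exclude a subject. Its haemoglobin line in the synopsis reads "Hemoglobin ≤10% of the lower laboratory reference range". Protocol 4.2 has the same limit, "10% of the lower laboratory reference range".

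Neighbouring lines in the list take three other forms:

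- a 10% tolerance around the range: "Platelets not within ±10% of laboratory reference range";
- a percentage distance with a named direction: "Alkaline phosphatase >20% above the upper laboratory reference range";
- no number at all: "White blood cell counts considered to be clinically significant by the investigator".

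Footnote (j) to the schedules in Appendix 2 gives these results their role: "Clinical laboratory testing from screening will be used to determine eligibility". Protocol 6.2.2 says that the central laboratory "will provide the reference ranges for all clinical laboratory safety parameters", but the documents do not print those ranges.

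Nothing elsewhere corrects the line. The Amendment 1 change history (Appendix 5) covers exclusions 7, 10, 32 and 34 but not 26. SAP 3.1.2 only points back to Protocol 4.2.

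**The concern.** A limit set at a tenth of the lower end of normal cannot be met by a living volunteer. The line looks like a safety screen for anaemia and has no effect.

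Three things hang on it.

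- **Eligibility.** This is the only numeric haemoglobin entry rule. A reader who rejects the literal number has to supply another, and the protocol offers none.
- **Deviations.** SAP 5.3 lists eligibility deviations, and Protocol 9.3.3.2.2 allows them to count as important. No realistic haemoglobin value can be a deviation from this line as printed.
- **Withdrawal.** One optional ground in Protocol 4.4.1 is a laboratory abnormality from the exclusion list. For haemoglobin that ground takes over the same unusable limit.

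Haemoglobin at entry has some practical weight, because PK subjects give repeated blood samples. Protocol 6 caps total collection at 500 mL. The PK schedule has 13 samples on Day 1, 1 on Day 14 and 15 from Day 28, which is 29 samples of about 5 mL, or roughly 145 mL before safety bloods.

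**Working it through.** The plan gives no derivation for this limit, so there is no figure to reproduce. The check is to put numbers into the line as printed and into its probable meaning.

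**Inputs**

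- Printed multiplier: 0.10 (criterion 26).
- Probable multiplier: 0.90, inferred from the platelet and alkaline phosphatase lines.
- Lower reference limit (LLN): not in the documents. Assumed 11 to 12 g/dL in women and 13 to 14 g/dL in men.
- DAIDS haemoglobin grades (Appendix 4). Women: grade 1 is 9.5 to 10.4, grade 2 is 8.5 to <9.5, grade 4 is <6.5 g/dL. Men: grade 1 is 10.0 to 10.9, grade 2 is 9.0 to <10.0, grade 4 is <7.0 g/dL.

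**Step 1. Cut-offs under each reading**

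| Assumed LLN (g/dL) | As printed, 0.10 x LLN | Probable, 0.90 x LLN | Printed cut-off as share of grade 4 threshold |
|---|---|---|---|
| 11 (women) | 1.1 | 9.9 | 1.1/6.5 = 17% |
| 12 (women) | 1.2 | 10.8 | 1.2/6.5 = 18% |
| 13 (men) | 1.3 | 11.7 | 1.3/7.0 = 19% |
| 14 (men) | 1.4 | 12.6 | 1.4/7.0 = 20% |

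**Step 2. The same conclusion without an assumed limit**

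The printed cut-off reaches grade 4 only if 0.10 x LLN equals the threshold. That needs LLN = 6.5/0.10 = 65 g/dL in women or 7.0/0.10 = 70 g/dL in men, five to six times the assumed limits (70/14 = 5.0; 65/11 = 5.9). No choice of reference range rescues the line.

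**Step 3. What the probable rule would add**

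At every assumed limit it would exclude all values of grade 2 or worse: the lowest cut-offs, 9.9 and 11.7, lie above 9.5 and 10.0. It would also exclude all of grade 1 in men, since 10.9 < 11.7. In women it would cover all of grade 1 only if the lower limit exceeds 10.4/0.90 = 11.56 g/dL.

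**Step 4. Candidate repairs**

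- Changing only *of* to *below* gives ≤10% below the lower limit. Read like the alkaline phosphatase line, where the sign governs the distance, that means a shortfall of at most 10%. With a lower limit of 12, it would exclude 10.8 to 12.0 g/dL and admit 8.0 g/dL, whose shortfall is (12 − 8)/12 = 33% and which is DAIDS grade 3 in women.
- Changing only 10% to 90% keeps the sign and the word *of*, and gives 0.90 x 12 = 10.8 g/dL.

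Both are one-token changes. The documents do not say which, if either, was the slip.

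**The case against.** The best case for leaving the line alone is that it does no harm in practice. A clinician is unlikely to apply a cut-off near 1.2 g/dL. Inclusion 5 requires good general health and names laboratory results as part of that judgement. Exclusions 7, 15 and 32 cover haematological disease, blood dyscrasia and general unsuitability, and exclusions 12, 13, 14 and 22 remove some causes of anaemia. Protocol 6.2.2 has abnormal values flagged against the reference range and reviewed for clinical significance. One laboratory supplies the ranges, and Protocol 9.3.1 provides for "protocol training and review of protocol procedures with the investigators and study site personnel before the start of the study". White cell count is left to judgement by design.

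Most of this stands, and it keeps the point small. It does not make the rule work. Central ranges fix the lower limit but not the multiplier, and the documents do not show that training covers this line. For white cells the plan openly chose judgement. For haemoglobin it chose a number, and the number has no effect.

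A reader might infer more than the documents support:

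- *Sites will differ, or anaemic subjects will be enrolled.* Possible, but nothing shows it, and the safeguards above point the other way. No anaemia prevalence is given, so no number of subjects can be stated.
- *The word* of *is the error.* Step 4 shows why this is conjecture.
- *Investigators lose a power to withdraw subjects.* They do not. The 4.4.1 grounds are permissive, and a separate ground for DAIDS grade 3 or 4 abnormalities applies to haemoglobin because 4.2 lists it.

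**Conclusion.** The haemoglobin line in criterion 26 is wrong as written, in both places. It excludes nobody under any lower limit that could occur. That conclusion rests only on the printed text and the protocol's DAIDS table.

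The probable intent, about 0.90 x the lower limit, is an inference from two neighbouring lines. The g/dL values (9.9 to 10.8 in women, 11.7 to 12.6 in men) also rest on the assumed reference limits.

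Severity is minor. The consequence is confined to eligibility screening, deviation reporting and one optional withdrawal ground. No sample size, primary analysis or comparison between arms changes. Confidence is high that the limit is unusable and only moderate on the intended value. Which word or number is misprinted remains unknown.

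**What to change.** In the synopsis and in Protocol 4.2, replace the line with: *Hemoglobin <0.90 x the lower limit of the laboratory reference range (more than 10% below it)*. Sex-specific g/dL values would serve as well. The sponsor's clinicians should confirm the value and whether the boundary is < or ≤; the two differ only at the exact cut-off. Do not simply swap *of* for *below*, because the result can be read as excluding only small shortfalls.

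The cost is two lines in the next protocol amendment, with submission to and approval by the central IRB (Protocol 9.3.3.2.1). No new test is needed, since haematology is already done at screening and used for eligibility. Protocol 4.4.1 and the SAP need no edit, because both refer to the exclusion list.
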